The outcomes will be assessed during the course of the inpatient admission through chart review. The timing of misoprostol placement will be accurately recorded by the nursing staff. Admission, fetal heart

rate tracing review, and delivery times will be recorded by the nursing staff. Adverse outcomes and maternal/fetal complications rates will be recorded prior to hospital discharge by chart review. Given that all outcomes will be evaluated at the time of inpatient admission, there will be no anticipated loss to follow-up.

Randomization

Randomization will occur according to a predetermined computer-generated stratified randomization scheme prepared by a study statistician. This method will be used to achieve balance among the intervention and control groups in terms of patients' characteristics including BMI >= 40 kg/m², parity, and intent to proceed with mechanical dilation at initiation of misoprostol placement. These three variables will be dichotomous such that there will exist a pre-stratified BMI >=40 kg/m² group, BMI <40 kg/m² group, multiparous group, nulliparous group, proceeding with mechanical dilation, and not proceeding with mechanical dilation. A separate block will be generated for each combination of covariates, and patients will be assigned to the appropriate block of covariates. When subjects have been identified and assigned into blocks, simple randomization will be performed within each block to assign subjects to one of the groups (control versus intervention).

Statistical Analysis

Descriptive statistics will characterize the group of individuals recruited to assess comparability of the treatment and control groups. Chi-Square test or Fisher's exact test will be used for categorical variables. Continuous variables will be examined for normality using the Shapiro-Wilk test; normally distributed continuous variables will be compared using the Student's t-test and those non-normally distributed will be compared using the Mann-Whitney U test. Analysis of the primary outcome will consist of a simple comparison of time from labor induction to delivery between the treatment and control group using generalized linear models. Stratified analyses will be used to identify potentially confounding effects. All tests will be two-tailed and use a significant level of <0.05. Data will be analyzed with the intention-to-treat principle.

[figure not shown]
Blinding

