This study will be double blinded with the research participants and providers/nursing masked to the interventions. A study statistician will create a randomization scheme as described above which will be utilized by the research pharmacy to distribute pre-packaged masked intervention packets.

Power Analysis

Sample size estimations were conducted using G*Power. Our analyses estimated a medium effect based on a 3-hour difference (SD=6) between our treatment (M=15 hours) and control (M=18 hours) groups⁴. These estimations were derived from the work of Carbone et al, Obstet Gynecol. 2013. We computed the required sample size to detect a medium effect with the specified parameters: strata = 8, power = 0.85, α =.05, f=0.25. This yielded a total sample size of approximately 180 participants total, 90 per group. Figure 1 depicts the relationship between sample size and effect size the study proposed. As effect size decreases, sample size increases.

Figure 1. Relationship between effect size and sample size for MD 30 RCT.

Future Plans

If our results demonstrate that 50mcg of vaginal misoprostol provides shorter interval time to delivery, is safe and well-tolerated, and has similar vaginal delivery rates compared to current induction methods, we will plan to seek funding for a multi-center trial to alter current induction methods for obese patients. This will provide a larger and thus more generalizable patient population to provide guideline recommendation changes.

Budget

To achieve a double-blind study, misoprostol doses will be provided as pre-quartered tablets of either 100 mcg tabs (to achieve 25 mcg) or 200 mcg tabs (50 mcg). These tablets are virtually indistinguishable in size. Ascension Hospital Research Pharmacy has provided significantly discounted rates to provide prepackaged blinded doses of misoprostol to this study. Their estimates include:

- Start-up fees \$1125
- Quarterly Maintenance \$100/month 100% = Agreed to discount for Fellow research project
- Combined Enrollment/Dispensing Fees \$150/subject 50% = \$75 x 180 subjects = \$13,500
- Misoprostol tablets 100mcg x 180 subjects = \$100
- Misoprostol tablets 200mcg x 180 subjects = \$100
- Close-out fees \$200
- Total Estimated Research Pharmacy Fees: \$15,025
- Document Translation Fees: \$500
- Standard medical grade weight scale: \$150 (approximate)
- Participant compensation: \$10 x 180 subjects = \$1800

Projected Total Costs: \$17,475

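### The stated pair of 180 participants and 85% power does not match the planned two-arm, two-sided test: those inputs need 146, and 180 gives about 92% power (a conservative error)

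*Combined protocol and SAP*

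**What the plan says.** The Power Analysis section reports a G*Power calculation for a medium effect, "based on a 3-hour difference (SD=6) between our treatment (M=15 hours) and control (M=18 hours"). The inputs are given as "strata = 8, power = 0.85", with alpha 0.05 and f = 0.25. The result follows directly: "This yielded a total sample size of approximately 180 participants total, 90 per group". The paragraph names neither the G*Power test nor the numerator df. It refers to Figure 1 for the relation between effect size and sample size; that figure was not available for this review.

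Three other sections bear on the calculation:

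- **Statistical Analysis:** "Analysis of the primary outcome will consist of a simple comparison of time from labor induction to delivery between the treatment and control group". The model class named for this is the generalized linear model. The section adds "All tests will be two-tailed" at the 0.05 level. For continuous variables in general it says "those non-normally distributed will be compared using the Mann-Whitney U test".
- **Randomization:** the stratification factors are BMI (cut at 40), parity and intended mechanical dilation. "These three variables will be dichotomous", so they form 2 × 2 × 2 = 8 strata.
- **Outcome Evaluation:** "there will be no anticipated loss to follow-up".

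**The concern.** The inputs agree with one another, but the output does not follow from them for the test that the plan describes. A comparison of two arms has 1 numerator df, and a standardised difference of 0.5 with 85% power at two-sided 5% needs clearly fewer than 180 participants.

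This is the plan's only statement of power. As written, it cannot be reproduced from the text and gives the wrong power for the primary comparison. A reader would take 3 hours as the difference detectable with 85% power, when 90 per arm can detect a somewhat smaller one. The Future Plans section foresees a multi-centre trial if results are favourable, and an unreproducible calculation should not be carried into its design.

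**Working it through.** **Inputs.** Difference 18 − 15 = 3 h, SD 6, alpha 0.05, power 0.85, f = 0.25, 8 strata and 90 per arm (Power Analysis); two-sided test of two arms (Statistical Analysis); no loss to follow-up expected (Outcome Evaluation).

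**Step 1: effect size.** d = 3/6 = 0.5. For two equal arms f = d/2 = 0.25, so the plan's f is reproduced.

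**Step 2: sample size for the two-arm test.**

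- Normal approximation: n per arm = 2(1.960 + 1.036)² × 6²/3² = 2 × 8.98 × 4 = 71.8, so 72 per arm (144 in total).
- Exact two-sample t: power is 0.846 with 72 per arm and 0.851 with 73, so 73 per arm (146 in total).
- Noncentral F with 1 numerator df, N − k denominator df for k groups, and noncentrality λ = f²N: N = 146, with λ = 0.0625 × 146 = 9.125. This holds for k = 2, 3, 8, 9 or 16. The number of groups enters only through the denominator df, so the 8 strata leave N unchanged.

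The stated 180 is not reproduced. The excess is 180 − 146 = 34, and 34/146 = 23%.

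**Step 3: power at 180.** λ = 0.0625 × 180 = 11.25. The noncentral F gives 0.915 to 0.916 for 2 to 16 groups, the exact t gives 0.916 and the normal approximation gives 0.918. For comparison, 1 df needs N = 171 for 90% power and 210 for 95%.

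**Step 4: which numerator df would give 180?** With f = 0.25, alpha 0.05 and 8 groups:

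| Numerator df | N for 85% power | Power at N = 180 |
|---|---|---|
| 1 | 146 | 0.916 |
| 2 | 178 | 0.854 |
| 3 | 201 | 0.804 |
| 4 | 220 | 0.760 |
| 5 | 236 | 0.721 |
| 6 | 251 | 0.686 |
| 7 | 264 | 0.655 |

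Only 2 df comes close (179 with 16 groups). Treatment and all three stratification factors are binary, so every single main effect or interaction has 1 df. An overall test across the 8 strata would have 7 df. Neither is a 2-df test.

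**Step 5: other routes to 180.**

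- *Dropout:* 146/(1 − 0.20) = 182.5, so 20% loss would give 183. The plan expects no loss and has no inflation step.
- *Other inputs:* 3 df at power 0.80 gives 179, and 1 df at alpha 0.025 gives 175. Each contradicts a stated input.
- *One-sided test:* 118, further away, and contrary to the plan.
- *Rank test:* dividing 146 by the efficiency of the Mann-Whitney test relative to the t test gives 146/0.955 = 153 (normal data) and 146/0.864 = 169 (worst case for a pure shift). Both fall short of 180.

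**Step 6: what 90 per arm provides.**

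- 85% power is reached at d = 0.449. That is 0.449 × 6 ≈ 2.7 h at SD 6, or 3 h at an SD up to 3/0.449 ≈ 6.7 h.
- With a Mann-Whitney test, power for 3 h at SD 6 is about 0.90 (normal data; 20,000 simulated trials agree) to 0.87 (worst case).
- With the t or F test, power for 3 h is 0.82 at SD 7 and 0.71 at SD 8. Both SDs are assumed values, not taken from the documents.

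**The case against.** The strongest reply is that little depends on this. Enrolment, the analysis and the significance threshold all stay the same, and the real power exceeds the stated power. That is true, and it is why the remedy is confined to wording; it does not make the stated figure correct.

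Figure 1 may show the G*Power test, the df or the number of groups. That is a fair limit on any claim that these details are absent from the plan, and the request to name them should be read with it. The mismatch does not depend on the figure, because no 1-df test at these inputs yields 180.

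A joint test of two terms, such as treatment plus one treatment-by-factor interaction, would have 2 df. So a 2-df test is possible in this design, but the documents do not say that one was powered, and it would not be the simple comparison of arms planned for the primary outcome. That 2 df was the source of 180 remains a guess.

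Finally, the Mann-Whitney sentence concerns continuous variables in general, while the primary outcome is assigned to generalized linear models. The rank-test figures are therefore conditional. They show that the choice of test does not rescue the stated pair.

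**Conclusion.** The point holds. For the planned two-sided, 1-df comparison, the stated inputs need 146 participants, not 180, and 180 gives about 92% power, not 85%. The arithmetic rests on the plan's own 3-hour difference, SD 6, equal allocation and complete follow-up, and on a normal outcome with common SD. Under a rank test at the same difference and SD, power would still exceed 85%.

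The direction is conservative: the trial is not underpowered on its own assumptions. The margin is limited, since power for 3 hours falls below 85% once the SD exceeds about 6.7 hours. The origin of 180 is unknown. This is a correction that should be made, not a threat to the trial's validity.

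**What to change.** Keep 180. In the Power Analysis section, name the G*Power test, the numerator df and the number of groups, and state that the 8 strata do not change the 1-df treatment test. Suggested replacement for the result:

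> With 90 participants per arm, a two-sided 5% test of the treatment effect (1 df, normal outcome with common SD) has about 92% power for a 3-hour difference if the SD is 6 hours, and 85% power for a difference of about 2.7 hours. Power for 3 hours is about 87–90% at SD 6 if a rank test is used, and 82% or 71% with the planned test if the SD is 7 or 8 hours (assumed values).

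If a rank test is ruled out for the primary outcome, omit that clause. Check Figure 1 against the same 1-df test and redraw it if it was produced with another df. The cost is protocol wording only, with no change in enrolment.
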